Purpose of the Study – The purpose of this study is to address the key question of whether and how family health history (FHH) is adopted as a tool to more efficiently manage patients at risk for breast, colon, ovarian, and hereditary cancer syndromes as well as thrombophilia and coronary heart disease (CHD) and to provide evidence supporting clinical utility -- improved health behaviors in patients and physician screening recommendations. Five health care delivery organizations will participate in this demonstration project: Duke University, the Medical College of Wisconsin, the Air Force, Essentia Health, and the University of North Texas Health Science Center. The study will take place in 'real world' clinical, socio-cultural, and demographically diverse (rural, underserved, academic, family medicine) clinics (n=34) in 5 states (CA, MN, NC, WI, TX) that include genomic medicine 'early adopter' and 'naïve' sites, as well as those that are EMR-enabled and others that are not, and will use a cluster randomized controlled pragmatic hybrid type III implementation-effectiveness observational study design. We anticipate enrolling **7000 English or Spanish speaking adult participants (at a minimum) over a 3-year period**; to reach this goal we need to enroll ~300 participants from each intervention clinic (assuming 10 of the 34 clinics will be dedicated controls). Specifically we will use Healthcare Effectiveness Data and Information Set (HEDIS) measures as intermediate clinical effectiveness measures for CHD and the selected cancers as well as survey/formative data and electronic medical record (EMR)

data as outcomes measures. The research model is purposely designed to mimic clinical delivery as an important step toward widespread implementation and sustainability. In addition we will use a cost-effectiveness analysis to compare usual care to the FHH guided preventive health model. **The completion of this project will result in an optimal strategy for integration of FHH data collection and clinical decision support (CDS) tools into an EMR and demonstrate the utility of the FHH intervention among diverse primary care patients, their settings, their providers, and the health systems that deliver their care.**

Specific Aim 1: To optimize the collection of patient entered FHH in diverse clinical environments for coronary heart disease, thrombosis, and selected cancers

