Resulting outcomes data, including all referrals, diagnoses, laboratory and genetic test results, medical procedures, office and ER visits, hospitalizations and medications that occur will be abstracted from patient medical record files prior to patient enrollment and throughout the study period by the participating clinics after patient participation has been concluded at each site and provided to the Duke statistical analysis team with only the patient's unique ID number.

Selection of Subjects –

Population: Study subjects will be comprised of providers and patients at the diverse clinics within in each of the 5 organizations (Duke University, Medical College of Wisconsin, Essentia Health, University of North Texas Health Science Center, and the Air Force).

Providers: all providers in the participating clinics will be selected to be included in the study. We anticipate 100% participation, for an expected enrollment of 365 providers.

ORCA survey participants will be providers, nurses, and administrators at participating clinics at each institution which are involved in MeTree implementation.

Key informants will be providers, nurses, and schedulers at each participating clinic which is involved in MeTree implementation.

Patients: All adult English or Spanish speaking patients scheduled for non-acute visits within 2 weeks will be invited to enroll when they schedule an appointment with their physician. Since this proposal focuses upon prevention and not disease management strategies, those with a study disease (breast, or colon cancer, hereditary cancer syndromes, or CHD) will not be excluded from enrollment but will be excluded from analyses relevant to their disease. We anticipate enrolling 7000 participants at a minimum (to achieve significance for effectiveness measures), but as an observational study will continue to enroll as many as are interested in order to maximize our ability to assess differences across settings, populations, and sociodemographic factors. To reach this goal we need to enroll ~300 participants from each intervention clinic (assumes 10 of the 34 clinics will be dedicated controls). Assuming 20% enrollment (from MeTree™ pilot -see preliminary data), we anticipate being able to enroll at least 9,100 participants.

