Patient recruitment will be initiated with requests to participate mailed when a well visit appointment is made or a reminder sent from the scheduling service at each intervention study site. Each invitation will include all the elements of informed consent, including a description of the study, its risks and benefits, further information about the surveys and description of the electronic consent process. Those who are interested will contact the central Duke study coordinator who may briefly review the study again. If the patient is interested, the Duke study coordinator will provide the participant with a web-based computer survey program account where they will complete the enrollment and consent process.

If the invited patients do not respond within the expected time window prior to their scheduled appointment the local site coordinators may follow up with a phone call to provide additional information about the study and to encourage their participation. If during this phone call patients express interest in enrolling the site coordinator will advise them to call Duke central office directly or will offer to contact Duke on their behalf. If latter, local site coordinators will collect/verify the following information and will submit in a secure email to [contact]:

- a. name (first, middle if any, last)
- b. email address (this will be the participants login, and to which all emails will be sent)
- c. did they set up this email specifically to participate in this study?
- d. institution
- e. verification that the participant is 18 years of age or older
- f. phone number
- g. gender
- h. date of birth
- i. clinic name
- j. provider name
- k. appointment date
- l. preferred language (English / Spanish)
- m. Medical record number or local unique identifier

Upon receipt of this information Duke study coordinator will complete the registration and notify participant via email. The local site coordinator will monitor this process in the site specific census.

There will be no compensation to provider, other clinic personnel, or patient participants.

Consent Process:

Providers will be consented in person by local study staff at each participating Institution after they have been provided with onsite education (by the local study staff) about the study and as to why they would want to participate. Should they agree, they will sign the consent form and receive an electronic survey link via email.

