Patients will be consented via an electronic consent process: each is provided via email a web-based computer survey program account in which a full version of the consent form is initially presented and electronically signed and dated by the participant to complete the consent process. Once signed, the participant is provided access to the baseline survey, the MeTree program for completion of family health history, and education about collection of FHH. Access to these online tools will be available from

computer or mobile device via the web or the clinic via a kiosk. In addition, a local study coordinator will be available for assistance.

Subjects' Capacity to Give Legally Effective Consent – Subjects who cannot give legally effective consent will not be included in the study since they would not be able to adequately perform the risk assessment or survey evaluations.

Study Interventions – see Design and Procedures section

Risk/Benefit Assessment –

Risks: Potential risks to the subjects include anxiety related to family health history results and breach of confidentiality of their study data. FHH data collection is already considered standard of care for medical practice and the risk associated with this information or risk-based prevention strategies is considered to be no more than that associated with routine clinical care. Patients and providers will discuss CDS output during their appointment and study and clinical staff are available if needed.

Provider participants do not have any anticipated risks.

The alternative for potential participants is not participating in the study.

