for multiple comparisons. Multivariate analysis will control for clinic and provider. A p-value of <0.1 in stepwise regression will identify significant factors such as demographics, intent to change, and their interactions. The analyses for the multiple outcomes will follow the same procedure as the survey outcomes but using a logistic regression model that includes the 7 covariate factors (see sample size section). Although the study is implemented at the level of the clinical practice, the likelihood of clustering is low given that all participants undergo the intervention and the intervention is aimed at both the patient and the provider; however, to address the possibility of clustering, we will calculate a design effect; if it is 1 we will use standard tests and generalized linear mixed models with clinic and state as random effects, if not we will adjust the confidence intervals using a conditional logistic regression. Effect size bias is extremely unlikely in this study as all individuals within the clinics are offered the intervention, preventing the imbalance in treatment assignment that can lead to inaccurate point estimates.

ORCA survey data will be analyzed using this validated survey's scoring method. The results will be used to categorize institutions and/or the individual clinics according to their flexibility for adapting to new ideas/technologies, which will then be included as an explanatory variable in the analysis of the effectiveness data captured during the trial as well as to help understand barriers encountered during the implementation process.

Key Informant Interview data analysis will proceed with an initial review of the transcripts conducted independently by study investigators. Each coder will identify major thematic categories included in the *a priori* theoretical model and emergent categories. The coders will work together to develop a revised schema for content coding. Once the schema has been finalized, the coders will code the transcripts for relevant categories and have discussions that may lead to further revision and refinement of the code book. Findings from the pre-implementation interviews will be used to create a tailored implementation plan at each site.

As of 01/20/2017 [name] is no longer on key personnel for this protocol, however she has been added to outside key personnel and will assist with writing study publications. She will see data summaries only, and not individual data.

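### Patient-reported outcomes come only from MeTree participants at intervention clinics, so their change over time has no concurrent usual-care comparator

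*Combined protocol and SAP*

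**What the plan says.** All references are to the combined protocol and SAP.

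- **Aim and design.** The Purpose of the Study seeks evidence of clinical utility in the form of "improved health behaviors in patients and physician screening recommendations". It describes the design as cluster randomized and controlled and, in the same sentence, as observational. It also plans an economic comparison: "In addition we will use a cost-effectiveness analysis to compare usual care to the FHH guided preventive health model".
- **Recruitment.** Under Subject Recruitment and Compensation, invitations accompany a well-visit booking or are reminders "sent from the scheduling service at each intervention study site".
- **Access.** Under Consent Process, one electronic signature opens both survey and intervention: "Once signed, the participant is provided access to the baseline survey, the MeTree program for completion of family health history".
- **Surveys.** Design & Procedures has each consented participant complete the baseline survey before the provider visit and repeat it at 3 and 12 months. SF12 and PAM are named as the instruments.
- **Exposure.** Data Analysis & Statistical Considerations states that "all participants undergo the intervention". It then argues that biased effect sizes are very improbable because everyone in the clinics is offered the intervention.
- **Controls.** Design & Procedures gives the control one role: detecting changes in standard clinical care. No section describes consent or surveys for control-clinic patients.

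**The concern.** A participant who reports better diet, more exercise or higher activation at month 3 or 12 has changed for some mixture of reasons. These include MeTree, the well visit that falls between baseline and follow-up, secular trend, being asked the same questions again, and regression to the mean. A concurrent usual-care group would share most of the non-MeTree parts and allow them to be subtracted. The plan has no such group for survey outcomes.

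At stake is what the study may conclude. A reader told that the design is cluster randomized and controlled, and that effect size bias is not a worry, could take a within-person survey change as a controlled estimate of benefit. The argument offered against bias, that everyone is offered the intervention, is also the reason there is no comparator. The family-history trial in 24 UK practices that Background & Significance presents as proof of concept compared behavior change with a control group. This plan's surveys cannot do that. The gap also cannot be closed afterwards, because activation or risk perception that was never asked about cannot be recovered from a medical record.

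**Working it through.** **1. Reproduce the enrolment target.** Selection of Subjects gives the target as "We anticipate enrolling 7000 participants at a minimum (to achieve significance for effectiveness measures" and builds it from about "300 participants from each intervention clinic (assumes 10 of the 34 clinics will be dedicated controls".

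- Intervention clinics: 34 − 10 = 24.
- 24 × 300 = 7200, which is 200/7000 = 2.9% above the stated 7000.
- In reverse, 7000/24 = 292 per intervention clinic, consistent with about 300.
- With other numbers of control clinics the figure does not reproduce: 5 controls give 29 × 300 = 8700, 1 gives 33 × 300 = 9900, and none gives 34 × 300 = 10,200.

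The intervention clinics therefore account for the whole target, and the planned number of surveyed control-clinic patients is 0. The 7000 is a minimum and at least 9,100 are anticipated, but the recruitment route is the same for the extra patients.

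**2. What the survey contrast estimates.** For a participant measured at baseline and month t:

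expected change = MeTree effect + visit effect + secular trend + repeat-questioning effect + regression to the mean.

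There is one observed mean and five unknown terms. If the last four sum to d, the whole of d is credited to MeTree.

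**3. Why sample size does not help.** The documents give no SD, ICC or dropout figure, so these are assumptions: complete follow-up, change expressed in SDs of change, and ICC from 0 to 0.05.

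- 95% half-width for mean change = 1.96 × √(design effect/7000), with design effect = 1 + (292 − 1) × ICC.
- ICC 0: 1.96/√7000 = 0.023 SD.
- ICC 0.01: design effect 3.91; 0.023 × √3.91 = 0.046 SD.
- ICC 0.05: design effect 15.55; 0.023 × √15.55 = 0.092 SD.

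With no MeTree effect at all, an observed drift larger than about 0.02 to 0.09 SD would be reported as a significant change. More patients shrink the interval around the same biased quantity.

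**4. Where a controlled contrast could come from.** The Purpose names HEDIS measures as intermediate effectiveness measures for CHD and the selected cancers, together with EMR outcomes. These could be extracted at control clinics. However, Design & Procedures defines record abstraction in relation to patient enrolment and participation, and it describes no extraction for control-clinic patients. Assumed enrolment is 20%, so setting enrolled volunteers against all control-clinic patients would also introduce self-selection.

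**The case against.** The strongest reply is that the documents repeatedly call the study observational, say that the surveys capture changes, plan descriptive statistics and associations, and give the controls only a limited role. On that reading nobody promises a controlled survey effect. Part of this stands: it would be a prediction, not a finding, to say that the sponsor will present before-after change as a trial effect. But the same Purpose section calls the design cluster randomized and controlled, no section labels the survey outcomes as uncontrolled, and the analysis section plays down bias. The reader is left without the caveat.

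Four stronger readings are tempting and are not supported:

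- **That the cost-effectiveness analysis lacks a usual-care arm.** No section says that SF12, PAM or any survey item enters it. HEDIS measures and record-based resource use are available candidates. What can be said is that its effect measure and usual-care data source are not stated.
- **That the health-behavior claim rests on surveys alone.** Background & Significance counts screening and use of preventive services among patient behaviors, and these can come from HEDIS/EMR data.
- **That diet and exercise come only from the survey.** Appendix A lists diet, exercise and tobacco as MeTree data elements. This supplies no comparator, since MeTree is given only to participants.
- **That the control clinics serve no purpose.** They could support a record-based contrast if their data are extracted.

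**Conclusion.** The point holds for patient-reported outcomes: there is no concurrent usual-care comparator. Planned surveyed controls number 0 against at least 7000 surveyed participants, so any drift shared by participants is attributed in full to MeTree. This rests on reading the recruitment, quota and consent sections together. The general sentence under Selection of Subjects about inviting all adult patients does not name intervention clinics, but the quota in the same section and the recruitment section restrict it to them. The size of the drift cannot be given from the documents, and the half-widths above depend on assumed ICCs and complete follow-up.

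The point does not extend to HEDIS/EMR outcomes. It reaches the cost-effectiveness analysis only in this sense: any usual-care term there must come from measures obtained in both groups of clinics.

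This should be corrected because it changes what the study may conclude, but it does not prevent the study from proceeding.

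**What to change.** 1. In the Purpose of the Study and in Data Analysis & Statistical Considerations, state that survey outcomes and MeTree-entered lifestyle data are uncontrolled before-after descriptions and are not by themselves evidence of effect. Remove the statement that effect size bias is improbable as it applies to them.
2. Rest claims of effect against usual care on HEDIS/EMR measures extracted the same way from intervention and control clinics. Compare all eligible patients by clinic assignment, not enrolled volunteers with control patients. State how control-clinic records are obtained, since abstraction is now tied to enrolled patients. State also that any usual-care term in the cost-effectiveness analysis comes from these both-arm measures.
3. While editing, reconcile the single comparator clinic in Design & Procedures with the 10 control clinics used elsewhere. Only 10 reproduces the 7000.

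**Cost.** The first change is wording, and its price is a narrower claim for survey outcomes. The second adds data-extraction work and some dilution: if only enrolled patients are affected, an effect e among them appears as about 0.20 × e across all eligible patients at the assumed 20% enrolment.

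Surveying control-clinic patients at 0, 3 and 12 months is a design option that would supply the missing comparator. It adds recruitment work and is not part of the required change.

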
Design & Procedures – This study will: 1) utilize a software platform entitled MeTree, which electronically captures participant-entered FHH and links to a web-based risk stratification and CDS system for prevention of CHD, breast cancer, colon cancer, and hereditary cancer syndromes. The risk stratification and CDS system pull together established, standard of care guidelines and validated risk calculators in one place to facilitate provider decision making. The output (pedigrees and reports with evidence-based risk stratified prevention recommendations) will be integrated into the EMR, and capture patient behaviors and attitude changes through a series of web-based computer surveys; and 2) provide just-in time education embedded within the CDS output to activate patients and providers and improve awareness of and adherence to FHH risk-stratification and risk-stratified prevention plans.

Multiple clinics at each participating institution will be recruited to participate, but providers will individually be able to participate at their own discretion. One comparator clinic will be randomly assigned as a “control” to be used to assess any changes in the standard clinical care between the participating clinics and the control.

This study will also include the administration of an Organizational Readiness to Change (ORCA) survey to identified personnel at each participating clinic, and followed by qualitative interviews for key personnel (Key informant interviews) identified at each participating clinic. .

ORCA survey design: an Organizational Readiness to Change Assessment (ORCA) will be administered as a survey by the Duke coordinating center personnel through a web-based electronic data capture program, with personnel in identified roles (provider, nurse, administrator) within participating clinics from each of the five health systems. Survey completion will occur prior to the implementation of the MeTree family health history tool, and will provide information about the organization’s climate and culture about integrating and implementing change.

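### Medical-record data from before enrolment are to be abstracted, but no effectiveness model is stated to adjust for them, so clinic baseline differences stay in any intervention-versus-control comparison

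*Combined protocol and SAP*

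**What the plan says.** Purpose of the Study describes a "cluster randomized controlled pragmatic hybrid type III implementation-effectiveness observational study design". It takes "Healthcare Effectiveness Data and Information Set (HEDIS) measures as intermediate clinical effectiveness measures" for coronary heart disease and the selected cancers, with survey and electronic medical record (EMR) data also serving as outcomes.

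The data paragraph at the end of Design & Procedures lists referrals, diagnoses, test results, procedures, visits and medications. These are "abstracted from patient medical record files prior to patient enrollment" as well as during follow-up, and go to the statistical team under the patient's study ID.

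On the comparator, Design & Procedures says "One comparator clinic will be randomly assigned". The stated role of this control clinic is "to be used to assess any changes in the standard clinical care between the participating clinics and the control". Purpose of the Study and Selection of Subjects instead count ten controls; the latter "assumes 10 of the 34 clinics will be dedicated controls".

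Data Analysis & Statistical Considerations analyses the multiple outcomes "using a logistic regression model that includes the 7 covariate factors" and refers to a sample size section for that list. It also names:
- control for clinic and provider;
- stepwise selection, with demographics and intent to change as examples;
- an organisational-readiness (ORCA) category as an explanatory variable;
- mixed models with clinic and state random effects if the design effect is 1, and conditional logistic regression otherwise.

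No intervention-versus-control term is written for any of these models.

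**The concern.** Asking whether care changed relative to a control is a before-and-after question, and the plan collects a before period. Yet no analysis described uses it as a covariate, a change score or a period term.

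The clinics are diverse by design, with rural, underserved and academic practices among them, so their usual screening and referral rates are likely to differ before anything is introduced. With 34 clinics, split unequally, randomisation can leave a material chance imbalance, and variation between clinics dominates the standard error. A clinic's earlier rate on the same measure is normally among the best predictors of its later rate. Leaving it out gives up precision and leaves a chance baseline difference in the estimate.

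**Working it through.** **1. The plan's own figure.** 34 − 10 = 24 intervention clinics. 7000 / 24 = 291.7 per clinic, against about 300 stated; 24 × 300 = 7200. This reproduces. The 7000 itself cannot be checked, because the supplied text gives no effect size, outcome rate, power or ICC.

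**2. Whether the stated terms already deal with baseline differences.**
- Clinic random effects put between-clinic variation into the standard error. They do not remove a baseline imbalance.
- Conditional logistic regression stratified by clinic, or fixed clinic effects, would absorb an arm effect that is constant within clinic.
- The ORCA category measures readiness for change, not earlier rates of care.
- The plan discounts imbalance because everyone within a clinic is offered the intervention. That does not address differences between intervention and control clinics.

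**3. Size of the gain.** Assumptions not in the documents: outcome rate p = 0.5; m = 291.7 patients in every clinic, controls included; ICC 0.01 to 0.05; clinic-level pre/post correlation r = 0.5 or 0.8. The 24 v 10 split follows from Purpose of the Study and Selection of Subjects.

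- Variance of a clinic mean: V = p(1 − p)[ICC + (1 − ICC)/m]
- SE = √[V(1/24 + 1/10)], where 1/24 + 1/10 = 0.1417
- Half-width = t(32 df) × SE, with t = 2.037
- Baseline as covariate: multiply the half-width by √(1 − r²), which is 0.866 at r = 0.5 and 0.6 at r = 0.8

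At ICC 0.02: V = 0.25 × (0.02 + 0.98/291.7) = 0.00584; SE = √(0.00584 × 0.1417) = 0.0288; half-width = 2.037 × 0.0288 = 5.9 points. Adjusted: 5.9 × 0.866 = 5.1 and 5.9 × 0.6 = 3.5.

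| ICC | Unadjusted | r = 0.5 | r = 0.8 |
|---|---|---|---|
| 0.01 | 4.4 | 3.8 | 2.7 |
| 0.02 | 5.9 | 5.1 | 3.5 |
| 0.05 | 8.8 | 7.7 | 5.3 |

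(95% half-widths in percentage points.)

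**4. A less favourable correlation structure.** Let r depend on the ICC: r = [ICC × CAC + 0.5(1 − ICC)/m] / [ICC + (1 − ICC)/m], with clinic autocorrelation (CAC) 0.8 and within-person correlation 0.5 (both assumed). Then r = 0.72, 0.76 and 0.78 at ICC 0.01, 0.02 and 0.05. The variance remaining is 48%, 43% and 39%, and the SE falls from 2.2 to 1.5, 2.9 to 1.9 and 4.3 to 2.7 points. At ICC 0.01 the half-width is 4.4 × √0.48, about 3.1 rather than 2.7. With CAC 0.5, 75% of the variance remains.

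**5. Arm-by-period model instead.** It leaves 2(1 − r) of the variance: 1.00 at r = 0.5 (no gain) and 0.40 at r = 0.8, against 0.75 and 0.36 for covariate adjustment. If it has a clinic random effect but no clinic-by-period effect, it treats clinic rates as stable over time. At ICC 0.02 and within-person correlation 0.5, compare the true and modelled variances of a clinic's change:
- CAC 0.5: true 2(0.02 × 0.5 + 0.00336 × 0.5) = 0.0234, modelled about 2 × 0.0034 = 0.0068. The SE is understated by a factor of √3.44 ≈ 1.9, and nominal 5% error becomes about 29%.
- CAC 0.8: true 2(0.02 × 0.2 + 0.00336 × 0.5) = 0.0114, modelled 0.0067. The factor is about 1.3, and the error about 13%.

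**6. Other readings of the control allocation** (ICC 0.02, CAC 0.8, 292 per clinic). One control per institution, 5 v 29: SE 3.7 to 2.4 points. One control in all, 1 v 33: SE 7.8 to 5.1 points.

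**The case against.** **The baseline may already be in the model.** A reader might infer that no effectiveness model uses the pre-enrolment data. The documents do not support that. The seven covariates are listed in a section that is not in the supplied text, and the stepwise candidates are given only as examples. A baseline measure could be among them. What stands is that none is stated.

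**The data may not exist for controls.** A reader might also infer that baseline records are in hand for every patient in both arms, so that adjustment needs no new data. Abstraction is tied to enrolment and a study ID, and Subject Recruitment and Compensation describes invitations only at intervention sites. Whether control-clinic records are abstracted, and for whom, is not stated. Without them, neither form of adjustment can be fitted to the arm comparison.

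**There is no arm comparison to mis-adjust.** The analysis section writes no arm term and reasons as though every participant receives the intervention. That is fair, and it is the larger gap: the contrast has to be defined before it can be adjusted. It does not make baseline adjustment unnecessary once that is done.

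**The illustration is generous.** It puts 291.7 patients in each control clinic too, implying 34 × 291.7 ≈ 9,917 records, while the 7000 is allotted to intervention clinics alone. The outcome rate, ICC and correlations are all assumed. The size is therefore indicative only.

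**Conclusion.** The point holds as a gap in specification. Pre-enrolment outcome data are planned, the control's stated purpose is to assess change, and no model is stated to use the baseline. The clinic terms that are named either leave baseline imbalance in place or risk absorbing the arm effect.

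Under the assumptions above, with 24 v 10 clinics, covariate adjustment shortens the half-width by about 13% at r = 0.5 and 40% at r = 0.8, whatever the ICC. With fewer control clinics the unadjusted error is larger and the need greater.

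A reader might go further and infer that the planned analysis is biased. Under randomisation it is not: this is mainly precision and protection against chance imbalance. It would become a bias question if control clinics were not truly randomised, or if control records were not selected in the same way as enrolled volunteers. The documents settle neither.

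**What to change.** In Data Analysis & Statistical Considerations:
- Write the intervention-versus-control contrast for each EMR/HEDIS outcome and list the seven covariates.
- Include as fixed covariates, whatever stepwise selection retains, the patient's own pre-enrolment status on the same measure and the clinic's pre-period rate.
- Keep clinic as a random effect and use inference suited to a small number of clusters.
- If an arm-by-period model is preferred, add a clinic-by-period random effect and do not present it as equivalent to covariate adjustment.

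In the data-abstraction paragraph of Design & Procedures, state that the same pre-period records are abstracted in control clinics, and for which patients. Reconcile the single comparator clinic in Design & Procedures with the ten controls in Purpose of the Study and Selection of Subjects.

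The cost is a few model terms and some clarifying sentences, plus the control-clinic pre-period extraction if it is not already planned.
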